Title: Promoting Viral Suppression Among Transgender Women Living With HIV in Santo Domingo

NCT #: NCT06316102

Date: October 8, 2025

Clinical Trial Protocol

Piloting a Multilevel Intervention to Promote Viral Suppression Among Transgender Women Living with HIV in Santo Domingo

Principal Investigator: [name], PhD, University of North Carolina at Chapel Hill

Sponsor/Collaborators: University of North Carolina, The George Washington University, Instituto Dermatológico y Cirugía de Piel (IDCP), National Institute of Mental Health

1. Administrative Information

Protocol Title: Piloting a Multilevel Intervention to Promote Viral Suppression Among Transgender Women Living with HIV in Santo Domingo

Principal Investigator: [name], PhD, University of North Carolina at Chapel Hill

Sponsor/Collaborators: The University of North Carolina at Chapel Hill, The George Washington University, Instituto Dermatológico y Cirugía de Piel (IDCP), National Institute of Mental Health

2. Background and Rationale

Transgender (trans) women across the globe experience a disproportionate burden of HIV with an estimated global HIV prevalence of 19%.^(1,2) In Latin America and the Caribbean, HIV prevalence among trans women is estimated between 18% and 38%, magnitudes of power higher than cisgender adult prevalence.^(3,4) Trans women also experience worse HIV care and treatment outcomes than cisgender adults, including lower rates of viral suppression.⁽⁵⁻¹¹⁾ Despite the implications of this for individual and population-level health, few interventions address the multiple social determinants of HIV outcomes among trans women.^(4, 7, 12-14)

Stigma is a key social determinant of HIV outcomes.^(14,15) Trans women experience intersectional stigma due gender identity, HIV status, and sex work.^(15,16) This intersectional stigma occurs in several forms: internalized stigma in the form of endorsing or applying negative beliefs; anticipated stigma in the form of fear that you will be discriminated or mistreated due to your identity; and enacted stigma in the form of actual mistreatment, exclusion, and discrimination.⁽¹⁷⁻¹⁹⁾ These multiple types and forms of stigma can negatively affect health among trans women, including HIV care and treatment outcomes.^(15, 20-22) Multilevel responses are needed to improve HIV outcomes among trans women by simultaneously and synergistically addressing individual, provider, and community dynamics.

3. Study Objectives

The purpose of the proposed study is to conduct a pilot randomized trial of the multilevel intervention GAP, or *Gender-affirming Abriendo Puertas*.

3.1 Primary Objective

Assess preliminary efficacy of GAP on viral suppression at 12 months.

3.2 Secondary Objectives

Examine pathways of influence (e.g. decreased stigma, increased cohesion) and experiences with the intervention to identify specific areas for improvement and scale up.

4. Study Design

This is a randomized control trial of the GAP intervention (Gender Affirming *Abriendo Puertas* (Opening Doors)). The GAP intervention includes four components that will be implemented over a 12-month period: 1) individual counseling; 2) peer navigation; 3) provider training and 4) community building. Upon consenting to enter the study, participants will be randomly assigned to the intervention arm (n=60) or the control arm (n=60). The assessment of the GAP intervention will be guided by a mixed methods design, including quantitative surveys, biological assessments, and qualitative interviews.

Both intervention and control participants will complete a baseline socio-behavioral survey and blood draw for viral load testing. These assessments will be repeated at midline (6 months) and endline (12 months). A sub-group of intervention participants (n=20) will be invited to participate in qualitative interviews at baseline, midline, and endline.

Intervention participants will be assigned a navigator upon completing baseline assessments. Navigators will maintain monthly communication (at a minimum) with intervention participants during the 12-month intervention period. Intervention participants will be scheduled for their first individual counseling session within two weeks following enrollment. During the second half of the intervention period (months 6-12), intervention participants will be invited to participate in community building activities hosted at two local trans organizations.

Control group participants will be contacted monthly by a member of the study team to facilitate retention and maintain contact information. They will not receive any other intervention. However, if a control group member attends a community building activity during months 6-12, they will not be turned away.

The study team will facilitate training in gender affirmative care with providers and staff at the HIV clinics where study participants receive care during the 12-month intervention period.

At midline and endline, intervention staff and HIV care providers will be invited to participate in focus groups to document their experiences with the intervention and recommendations for improvement.

5. Study Population

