7.1 Primary Outcome

Viral suppression (<400 copies/mL)

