7.2 Secondary Outcomes

HIV care and treatment outcomes: Retention in HIV care, ART adherence , ART interruption

Mental health and wellbeing outcomes: Depression, anxiety, drug use, binge drinking, self-esteem

8. Study Procedures

Participants will complete assessments at baseline, midline, and endline. Data collection includes completion of a survey and blood draw for viral load measurement. Qualitative data collection will involve in-depth interviews with 20 participants from the intervention group at baseline, midline, and endline.

9. Statistical Considerations

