To estimate the initial effects of GAP, we will use survey, viral load, and monitoring data. We will first examine if randomization succeeded by conducting balance tests with baseline data, which will also inform the specification of the effects estimation model. Second, we will examine loss-to-follow-up (LTF) (expected not to be >10%) and determine if those LTF have different characteristics of those retained and if there is any variation between intervention and control groups. Third, we will estimate initial effects of the intervention. We will first estimate the intention-to-treat (ITT) effect using linear probability (or logistic) model with a GAP intervention indicator as the only explanatory variable and using endline data only. The ITT model will be $Y_i = \alpha_0 + \alpha_1 P_i + \varepsilon_i$, where Y_i is the outcome of individual i , P_i is a dummy indicator variable for being in the treatment group or not, and ε_i is the standard error term. The coefficient α_1 will be our ITT effect estimate. Although the GAP intervention will be randomly allocated across participants, it is possible that some differences in baseline characteristics and outcomes between the groups will be observed. To correct for those imbalances, we will use difference-in-differences (DID) models that include baseline covariates; the DID model estimates intervention effects by taking the difference between the changes observed in the outcome in the intervention group and the changes in the control group, adjusting for baseline differences. The DID model will be estimated using baseline, midline, and endline data and will be specified as: $Y_{it} = \alpha_0 + \alpha_1 P_i + \alpha_2 T1_t + \alpha_3 P_i * T1_t + \alpha_4 T2_t + \alpha_5 P_i * T2_t + \alpha_6 X_i + \varepsilon_{it}$, where Y_{it} is the outcome of individual i at time t , P_i is an indicator variable for being in the intervention group or not, $T1_t$ is an indicator variable for the observation from midline, $T2_t$ is an indicator variable for the observation from endline, X_i represents characteristics of the individual at baseline, and ε_{it} is the standard error term. The coefficient α_3 will be our DID intervention effect at

midline, and α_5 at endline. This DID model allows us to examine the evolution of the intervention effects over time.

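### Randomisation is placed at consent, on the natural reading before baseline, with nothing withholding the allocation; an arm-specific, transient reporting shift at baseline would bias the difference-in-differences estimates for survey outcomes.

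*Protocol*

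**What the plan says.** Section 4 (Study Design) of the protocol gives the sequence in this order:

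- Allocation: "Upon consenting to enter the study, participants will be randomly assigned to the intervention arm (n=60) or the control arm (n=60".
- Baseline, described by arm: "Both intervention and control participants will complete a baseline socio-behavioral survey and blood draw for viral load testing".
- Baseline interviews, offered in one arm only: "A sub-group of intervention participants (n=20) will be invited to participate in qualitative interviews at baseline, midline, and endline".
- Navigator: "Intervention participants will be assigned a navigator upon completing baseline assessments".

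Neither Section 4 nor Section 8 (Study Procedures) reverses this order, and neither says when participants or interviewers learn the arm.

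Section 9 (Statistical Considerations) gives baseline data three uses. The first is a check on the randomisation: "We will first examine if randomization succeeded by conducting balance tests with baseline data", a check that also shapes the effects model. The second is as covariates X_i in the DID model. The third is as the reference time point of that model, where alpha_3 is the effect at midline and alpha_5 the effect at endline. The ITT model is different. It is fitted "with a GAP intervention indicator as the only explanatory variable and using endline data only".

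The primary outcome in Section 7.1 is a laboratory measure: "Viral suppression (<400 copies/mL". The mental health and wellbeing outcomes in Section 7.2 are "Depression, anxiety, drug use, binge drinking, self-esteem". Section 7.2 also lists adherence and treatment interruption, and Section 3.2 names stigma and cohesion as pathways. The instruments are not stated. I assume that most of these measures come from the survey.

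**The concern.** Each use of baseline in Section 9 presupposes values that allocation could not have influenced. If a woman knows her arm when she answers the baseline survey, that no longer holds for self-reports. Someone just offered counselling and a navigator may describe her mood, drinking or adherence differently from someone just told she is a control.

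Three things are then at stake. The DID model was chosen to remove chance imbalance, so it would treat a reaction to allocation as imbalance and subtract it. A balance test could no longer separate chance from reaction. And a woman who is randomised but never completes baseline has no X_i, so she falls out of the covariate-adjusted DID although she was allocated; if that loss is linked to the allocation, it can differ by arm.

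**Working it through.** **1. The order.** Set side by side, the Section 4 statements fit one sequence best: consent and allocation, then baseline, then navigator. The baseline interviews are the strongest support, because they can be confined to intervention participants only if arm is settled by the baseline stage. The navigator sentence delays the navigator, not the allocation.

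**2. How a baseline shift enters the DID.** With arm-by-time indicators, and I and C the arm means,

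alpha_5 = (I_end − C_end) − (I_base − C_base),

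and alpha_3 is the same with midline in place of endline. In the linear model with complete data this is exact: X_i does not vary over time, so it leaves alpha_3 and alpha_5 unchanged (I confirmed this on a simulated three-wave panel). Add a shift b to the intervention arm at baseline:

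- b at baseline only: alpha_5 moves by −b.
- b at baseline and unchanged at endline: alpha_5 does not move; the endline-only ITT moves by +b instead.
- the same b in both arms at baseline: it cancels.

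A simulation agrees. Inputs are 54 women per arm, an assumed true effect of 0.10, an assumed control rate of 0.50 and 2,000 runs per setting.

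| Baseline shift, intervention arm | DID, shift gone by endline | ITT, shift gone by endline | DID, shift persists | ITT, shift persists |
|---|---|---|---|---|
| −0.10 | 0.20 | 0.10 | 0.10 | 0.00 |
| −0.05 | 0.15 | 0.10 | 0.10 | 0.05 |
| +0.05 | 0.05 | 0.10 | 0.10 | 0.15 |
| +0.10 | 0.00 | 0.10 | 0.10 | 0.20 |

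**3. What such a shift does to the test.** The protocol gives no figure on this point, so there is none to reproduce. Inputs:

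- Women per arm: 120 × 0.9 / 2 = 54, from the sample size and 10% loss in Section 9.
- Scale: continuous, in SD units (assumption).
- Baseline-endline correlation rho: 0.4 to 0.7 (assumption).
- Shift b: 0.1 or 0.2 SD, one arm, baseline only (assumption).

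For a two-wave change score, SE = sqrt(2(1 − rho) × 2/54), and type I error = P(|Z + b/SE| > 1.96).

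At rho = 0.5: SE = sqrt(1 × 2/54) = 0.192; b/SE = 0.2/0.192 = 1.04; type I error = 18.0%.

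| rho | SE | b = 0.1 SD | b = 0.2 SD |
|---|---|---|---|
| 0.4 | 0.211 | 7.6% | 15.8% |
| 0.5 | 0.192 | 8.1% | 18.0% |
| 0.6 | 0.172 | 8.9% | 21.3% |
| 0.7 | 0.149 | 10.3% | 26.9% |

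**4. Women without baseline.** The DID in Section 9 is a pooled regression without individual fixed effects. A woman who lacks only the baseline outcome still supplies midline and endline rows. One who skips baseline altogether has no X_i and drops out, unless X_i is imputed. She stays in the endline ITT if seen at 12 months.

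**The case against.** The strongest reply is that the protocol never says arm is known at baseline. Protocols routinely label participants by arm at every time point, and the first arm-specific contact dated for all intervention participants, the navigator, follows baseline. This stands. A reader might infer that baseline answers are given in knowledge of the arm; the text shows only that the allocation is made by then and that no step withholds it.

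A reader might also infer that any reporting shift biases the DID. It does not: common shifts and persistent shifts cancel. Indeed, if knowing one's arm alters self-reports lastingly, collecting baseline before disclosure leaves that shift in follow-up alone, and the DID then carries it, as the endline ITT already would. Early baseline is sound practice but does not cure unmasked follow-up.

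Third, the primary objective is viral suppression at 12 months, measured in blood, and the ITT uses no baseline value. That stands too: nothing here shows the primary ITT result to be compromised. Finally, the shift sizes and correlations are assumed, some outcomes may be binary, and the protocol calls the study a pilot. This limits what the percentages prove, but not the weakness in the sequence.

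**Conclusion.** The point holds in limited form. Section 4 fixes randomisation at consent, on its natural reading before baseline, and provides no withholding of the allocation, while Section 9 relies on baseline as untouched by it. If arm is known at baseline, a shift that differs by arm and has faded by follow-up biases alpha_3 and alpha_5 one for one on survey-based secondary and pathway outcomes.

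On the assumed values above, type I error rises from 5% to about 18% at 0.2 SD and rho 0.5 (16% to 27% across rho), and to 8% to 10% at 0.1 SD. These are illustrations; the protocol gives no basis for the size of a shift, or for whether one occurs. The balance tests become harder to interpret, and women who skip baseline are lost from the covariate-adjusted DID. The endline-only ITT on viral suppression is not directly affected. The change is worth making because it costs little, not because bias has been shown.

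**What to change.** Change Section 4 to: consent; then baseline survey and blood draw; then randomisation. If allocation must be generated earlier, state that it is disclosed to participant and interviewer only after both assessments are complete. The baseline interviews with intervention participants would then follow disclosure.

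Where women have already been enrolled under the other order, state the order actually used and when the arm was disclosed, and read the balance tests and the DID on self-reported outcomes with that caution. If practice already follows the safer order, only the text needs correcting.

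The cost is a reordering of enrolment steps, with no added participants and no change to the sample size. Women who consent but do not finish baseline would simply not be randomised. Follow-up self-reports remain unmasked, so the change protects baseline only.

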5.1 Inclusion Criteria

- Age \geq 18 years
- Assigned male at birth and self-identify as trans woman (using locally appropriate terminology)
- HIV-positive (confirmed by rapid test)

5.2 Exclusion Criteria

- Participation in the GAP adaptation study

5.3 Recruitment

Peer navigators will lead recruitment through social networks, referrals, and HIV clinics. The target sample size is 120 participants.

6. Intervention

The GAP intervention includes 4 intervention components:

1) Individual counseling and health education includes 4 sessions facilitated by a trained psychologist. Sessions address internalized stigma through reflective exercises, active listening, relaxation and stress management, information provision and, as needed, referrals to other services such as substance use and violence support. We also aim to promote key concepts from healthcare empowerment including being informed, committed, collaborative and engaged in healthcare. Self-esteem is a cross-cutting theme addressed in all sessions through critical reflection exercises.

Each session is structured around a topical focus and guided by objectives:

- Session 1: Gender identity and sexual health
- Session 2: Managing life with HIV
- Session 3: HIV care and treatment
- Session 4: Life plan

Each session concludes with a relaxation exercise intended to provide a set of tools for participants to use beyond the intervention.

All content will be delivered with sensitivity to the lived experience of trans women. Within each session, the content is flexible and tailored to the needs and interests of the specific participant. Screening for substance use and violence is integrated into sessions 1 and 2 to facilitate tailoring of content and referral to appropriate services as needed. Participants will be asked about their engagement with the trans community to assess their level of connection and identify opportunities to promote engagement or address concerns with engagement, in preparation for the community building component of GAP.

Sessions will be scheduled at one to two-week intervals to facilitate cumulative progression in stigma reduction and self-esteem building. Participants will have the option to do the sessions at IDCP or TRANSSA.

2) Peer navigation is a strengths-based model to address both internalized and enacted stigma. Navigators will provide informational, instrumental, and emotional support for HIV-related and other life concerns through in-person and virtual (e.g. text, WhatsApp) interactions. Examples of activities that navigators carry out include: appointment reminders; accompaniment to HIV and other medical appointments; supporting disclosure to family, friends and partners; and referral to services as needed. Navigators will also work with participants to address barriers to accessing care, develop strategies to use their existing resources and cultivate additional resources to maintain health and well-being, and, when needed, advocate for their rights.

As noted earlier, we will offer the option of having a trans or cisgender peer navigator. We will have a team of 3-4 navigators with approximately 15-20 intervention participants and 15-20 control participants assigned to each navigator. Navigators will be trained in HIV care and treatment and strengths-based approaches and will meet weekly as a team to exchange experiences and address challenges. While the actual intervention strategy of navigation will serve as a tool for retention with intervention participants, navigators will also support retention among control-group participants through regular check ins and reminders about study visits. As navigation can be initiated by either the navigator or client, there will be variation in the number of navigation interactions per participant. Navigators will be trained to initiate at least one interaction per month with each client, leading to a minimum of 12 interactions during the intervention period.

3) Provider capacity building will focus on enacted stigma in HIV clinics through training in gender affirmative care (GAC). GAC in HIV clinics includes both social and medical affirmation. We will focus on both, though medical gender affirmative care is not currently available in the 8 HIV clinics that we will work with. We will facilitate a two-day participatory workshop informed by evidence-based models of GAC¹⁴ with 4-5 participants from each clinic including providers (n=2), phlebotomist (n=1) and other staff who engage with trans participants (n=2). We will raise awareness, identify biases and misconceptions, and work with participants to develop individual and clinic-level plans to improve the overall quality of the clinic experience for trans women. During the training, each clinic will also do a self-assessment of readiness to integrate hormone therapy.

Study staff will facilitate a one-day booster session to assess application of the workshop content. Pre and post-assessments will be conducted at both workshops to document changes in attitudes and practices related to GAC and participants will be asked to provide updates to their readiness assessment at the booster session. Study staff will document clinic context during site visits to contextualize study findings on enacted stigma in HIV clinics. As noted earlier, provider capacity building will potentially affect both intervention and control groups as we will train providers from clinics attended by control and intervention groups.

4) Community Support Building will focus on developing trust through a series of small group sessions. These sessions will begin at midline. This will be done through a combination of structured content, participatory exercises, and social interaction. Each month will have a topical focus, which will be decided upon in response to feedback from the psychologists facilitating individual sessions, navigators, and participants themselves, to make the sessions highly responsive to gaps in other intervention components and participant interest. Expected topics include sustaining ART adherence, relationships, employment, and family dynamics. Sessions focused on the monthly topic will be repeated three times each month with the goal that each intervention arm participant (n=60) will attend at least one group session per month for a total of 6 sessions during the intervention period.

Control Arm: Standard HIV care, with potential indirect exposure to provider training.

7. Outcome Measures

7.1 Primary Outcome

Viral suppression (<400 copies/mL)

7.2 Secondary Outcomes

HIV care and treatment outcomes: Retention in HIV care, ART adherence , ART interruption

Mental health and wellbeing outcomes: Depression, anxiety, drug use, binge drinking, self-esteem

8. Study Procedures

Participants will complete assessments at baseline, midline, and endline. Data collection includes completion of a survey and blood draw for viral load measurement. Qualitative data collection will involve in-depth interviews with 20 participants from the intervention group at baseline, midline, and endline.

9. Statistical Considerations

To estimate the initial effects of GAP, we will use survey, viral load, and monitoring data. We will first examine if randomization succeeded by conducting balance tests with baseline data, which will also inform the specification of the effects estimation model. Second, we will examine loss-to-follow-up (LTF) (expected not to be >10%) and determine if those LTF have different characteristics of those retained and if there is any variation between intervention and control groups. Third, we will estimate initial effects of the intervention. We will first estimate the intention-to-treat (ITT) effect using linear probability (or logistic) model with a GAP intervention indicator as the only explanatory variable and using endline data only. The ITT model will be $Y_i = \alpha_0 + \alpha_1 P_i + \varepsilon_i$, where Y_i is the outcome of individual i , P_i is a dummy indicator variable for being in the treatment group or not, and ε_i is the standard error term. The coefficient α_1 will be our ITT effect estimate. Although the GAP intervention will be randomly allocated across participants, it is possible that some differences in baseline characteristics and outcomes between the groups will be observed. To correct for those imbalances, we will use difference-in-differences (DID) models that include baseline covariates; the DID model estimates intervention effects by taking the difference between the changes observed in the outcome in the intervention group and the changes in the control group, adjusting for baseline differences. The DID model will be estimated using baseline, midline, and endline data and will be specified as: $Y_{it} = \alpha_0 + \alpha_1 P_i + \alpha_2 T1_t + \alpha_3 P_i * T1_t + \alpha_4 T2_t + \alpha_5 P_i * T2_t + \alpha_6 X_i + \varepsilon_{it}$, where Y_{it} is the outcome of individual i at time t , P_i is an indicator variable for being in the intervention group or not, $T1_t$ is an indicator variable for the observation from midline, $T2_t$ is an indicator variable for the observation from endline, X_i represents characteristics of the individual at baseline, and ε_{it} is the standard error term. The coefficient α_3 will be our DID intervention effect at

midline, and α_5 at endline. This DID model allows us to examine the evolution of the intervention effects over time.

A second set of analyses will examine the effect of each component of the intervention on the main outcome at midline and endline. We will estimate the following model: $Y_i = \alpha_0 + \alpha_1 P1_i + \alpha_2 P2_i + \alpha_3 P3_i + \alpha_4 X_i + \varepsilon_i$ where $P1_i$ is a measure of individual counseling (e.g. # of counseling sessions individual i received); $P2_i$ is a measure of navigation (e.g. # of interactions with individual i); and $P3_i$ is a measure of community support building (e.g. # of group sessions attended by individual i). We will further extend this model to examine if different levels of intensity of exposure have different effects on the outcome. We will define three levels of intensity (low, medium, high) depending on the number of navigation interactions to estimate the following model: $Y_i = \alpha_0 + \alpha_1 P1_i + \alpha_{2Med} P2Med_i + \alpha_{2High} P2High_i + \alpha_3 P3_i + \alpha_4 X_i + \varepsilon_i$ where, $P2Med_i$ is a dummy variable indicating that individual i had medium exposure to navigation and $P2High_i$ is high intensity exposure to navigation sessions. In this model, α_{2Med} is the effect of medium exposure to navigation on the outcome and α_{2High} is the effect of high exposure to navigation on the outcome. The reference category is low exposure.

The minimum detectable effect for a power of 80%, a significant level of 5%, and a 50/50 split of the 120 individuals in the sample between the treatment and control group is of +13.3 percentage points, assuming an expected loss to follow up of 10%, and expected baseline prevalence of viral suppression to be 64%.

10. Data Management and Monitoring

Confidentiality of all study participants will be strictly maintained across all study activities. Interviewers, intervention staff, lab staff, support services staff, and all other relevant project staff will be trained on procedures for maintaining confidentiality. Interviewers assigned to conduct the survey assessments and qualitative interviews and focus groups will be hired by IDCP, which has a longstanding history of conducting confidential and respectful HIV-related research activities with key populations. All study data, laboratory specimens, and forms will be identified by a coded participant ID number only, to maintain participant confidentiality.

After study completion, identifying information for participants not required for analysis will be destroyed. Forms, lists, logbooks, appointment books, and any other listings that link participant ID numbers to other identifying information will be stored on a secure, password protected computer in a locked study office at IDCP in the DR, in an area accessible only to authorized study personnel.

11. Ethical Considerations

This study does not raise major safety concerns. However, we will continually monitor wellbeing of both intervention and control group participants. Safety analyses will be included as part of the regular reports to the safety team, composed of all of the key investigators and chaired by the study PI. The safety team will review all social harms reported at their monthly meetings. However, the PI will review the reports in real-time, and should any worrisome pattern or serious harm occur to a study participant as a result of their participation, she will call an ad hoc meeting of the safety team. We will query specifically for known social harms, including stigma, rejection by family and friends, or other adverse events. Intervention participants will meet with study counselors during the first part of the study and will have continuous contact with peer navigators. These interactions will permit monitoring of overall health and wellbeing. Control group participants will be contacted on a monthly basis by a study team member.

12. References

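### Neither planned 12-month effect model adjusts for baseline viral suppression: one ignores it, the other subtracts it in full, and both lose precision on the risk-difference scale

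*Protocol*

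**What the plan says.** The primary outcome is binary ("Viral suppression (<400 copies/mL", section 7.1), and the primary objective concerns 12 months (section 3.1). Section 4 has baseline viral load measured in everyone: "Both intervention and control participants will complete a baseline socio-behavioral survey and blood draw for viral load testing".

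Section 9 then sets out the effect analysis in this order:

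- **Balance tests.** Randomisation is checked by "conducting balance tests with baseline data, which will also inform the specification of the effects estimation model".
- **Endline-only model.** "We will first estimate the intention-to-treat (ITT) effect using linear probability (or logistic) model", fitted "with a GAP intervention indicator as the only explanatory variable and using endline data only". The effect is α₁.
- **DID model.** "To correct for those imbalances, we will use difference-in-differences (DID) models that include baseline covariates". It uses all three waves, with arm, wave, arm-by-wave terms and baseline characteristics X_i. The 12-month effect is α₅. The protocol adds: "This DID model allows us to examine the evolution of the intervention effects over time".

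The later models in section 9 also carry X_i, but they estimate exposure to intervention components, not the effect of the randomised arm. No stated model for the arm effect regresses endline suppression on arm plus baseline suppression.

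**The concern.** In a randomised trial, a chance baseline difference D in suppression carries through to endline only in part, by about rho × D. Ignoring it leaves rho × D in the estimate. Subtracting all of it leaves -(1-rho) × D, which is an over-correction. The two planned estimates therefore err in opposite directions, and with complete data they differ by exactly D. Neither is biased over repeated randomisation; what is lost is precision. That matters here because only about 54 per arm are expected at endline, and the measurement that would recover some precision is already taken.

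Letting balance tests shape the model adds a second weakness: whether a covariate enters would depend on the data. Under valid randomisation a 5% test of baseline suppression flags about 5% of trials, whereas the gain from adjustment does not depend on a flag.

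**Working it through.** **Inputs from the protocol.** 120 randomised 1:1; 10% loss, so 60 × 0.9 = 54 per arm; 64% suppression; effect +13.3 points, so 64% vs 77.3%; 5% significance, taken as two-sided. **Not in the protocol:** rho, the correlation between baseline and 12-month suppression. A range is shown.

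**The plan's own figure.** Section 9 gives a minimum detectable effect of "13.3 percentage points, assuming an expected loss to follow up of 10%, and expected baseline prevalence of viral suppression to be 64"%. This does not reproduce. At 54 per arm the two-sided detectable difference at 80% power is 22.9 points (20.7 one-sided). Power for 64% vs 77.3% is about 33%. That is a separate defect. It is used here only as the protocol's own effect size.

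**Weights.** The endline-only model contains no baseline term, so its weight on baseline is 0. In the DID model with complete data, α₅ is the raw difference in changes, so the weight is 1. X_i does not vary over time, so it cannot alter α₅. An ordinary least-squares fit confirmed this even with baseline suppression itself as X_i, and a three-wave simulation agreed to rounding error.

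**Variances.** Take a common variance σ² = 0.64 × 0.36 = 0.2304 and n = 54 per arm.

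- Endline-only: 2σ²/n = 0.4608/54 = 0.00853, SE 9.24 points.
- DID: the same × 2(1-rho).
- Endline adjusted for baseline: the same × (1-rho²).

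Since (1-rho²) - 2(1-rho) = -(1-rho)², the adjusted variance is below the DID variance for every rho < 1. It is below the endline-only variance for every rho > 0. DID is worse than no adjustment when rho < 0.5. These are large-sample results.

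**Simulation.** 20,000 trials per setting, 54 per arm, 64% vs 77.3%, robust SEs. Ranges run over three generating models: equal correlation in both arms, latent probit, and random conversion of unsuppressed to suppressed in the treated arm. Variances are relative to endline-only.

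| rho | DID variance (formula) | Adjusted variance (formula) | Adjusted variance (simulated) | Power, endline-only | Power, DID | Power, adjusted |
|---|---|---|---|---|---|---|
| 0.2 | 1.60 | 0.96 | 0.97-0.98 | 32-34% | 21-22% | 33-35% |
| 0.3 | 1.40 | 0.91 | 0.92-0.94 | 32-34% | 22-24% | 34-36% |
| 0.5 | 1.00 | 0.75 | 0.76-0.82 | 32-34% | 28-31% | 38-41% |
| 0.7 | 0.60 | 0.51 | 0.51-0.64 | 32-34% | 38-47% | 48-57% |

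Type I error of the adjusted model was 4.6-4.9%. By the formula, 54 adjusted per arm is worth 54/(1-rho²) = 56, 59, 72 and 106 unadjusted. Using the simulated ratios instead (54 divided by each) gives 55-56, 57-59, 66-71 and 84-106.

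**Chance imbalance.** D has SD 9.2 points, and a difference of 10 points or more in either direction occurs in about 27% of trials. A 5% test needs roughly 1.96 × 9.24 = 18.1 points to flag, so most such imbalances pass it. Simulated slopes of each estimate on D, with no treatment effect:

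| rho | Endline-only | DID | Adjusted |
|---|---|---|---|
| 0.3 | 0.29 | -0.71 | -0.01 |
| 0.5 | 0.50 | -0.50 | 0.00 |
| 0.7 | 0.71 | -0.29 | 0.01 |

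At D = +10 points and rho 0.5, endline-only is off by about +5 points, DID by about -5 and the adjusted estimate by about 0.

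**The case against.** The strongest reply is that nothing in section 9 is false. An unadjusted comparison followed by DID is valid under randomisation, the harm is efficiency only, and its size rests on a correlation the protocol does not give. This is a pilot of preliminary efficacy, and a few points of power on an underpowered comparison change little. Which estimate ranks first may be settled in the SAP, and section 9 does put the endline-only model first.

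Much of this stands as a limit on size:

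- At 54 per arm there is no gain when rho is about 0.1 or below (simulated SE 9.28 adjusted vs 9.24 at rho 0; equal at 0.1).
- The power gain is about 1 point at rho 0.2 and 2-3 points at 0.3.
- The formula-based equivalent sample sizes are the favourable end; the simulated ranges are the fairer guide.
- The rho 0.7 row should not be read as typical. With 64% at baseline and 77.3% at endline, the treated-arm correlation cannot exceed √(0.64 × 0.227 / (0.36 × 0.773)) = 0.72.
- The weights and variances hold for the linear model. They do not carry over to the logistic option.

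It does not remove the point. The protocol does not leave the adjustment open: it fixes arm as the sole regressor, and it offers DID as the cure for imbalance, which DID over-corrects. The missing ranking of the two estimates is not needed for the conclusion.

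**Conclusion.** The concern holds. On the risk-difference scale, adjusting the endline comparison for baseline suppression is more precise than both planned estimates unless rho is close to 0, where it matches the endline-only model, or close to 1, where it converges with DID. The power gain over endline-only is 6-9 points at rho 0.5 and 15-24 at 0.7.

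This assumes valid randomisation, 54 analysed per arm and the protocol's 64% rate; the weight of exactly 1 in DID also assumes complete data and is approximate with dropout. It is a loss of efficiency, not a bias. It does not rescue the stated detectable effect: under the common-variance formula, reaching 13.3 points would need rho of about 0.86 with adjustment or 0.87 with DID. It should be changed because the gain is nearly free, but it does not invalidate the trial.

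**What to change.** Prespecify as the main intention-to-treat analysis endline suppression on arm plus baseline suppression. Use either a linear probability model with robust SEs or a logistic model reported as a standardised risk difference, because the adjusted odds ratio is a conditional quantity. Fix this regardless of the balance tests, and use balance tables descriptively. Keep the crude endline comparison as a sensitivity analysis.

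If a three-wave model is wanted to show effects over time, do one of the following:

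1. Model only the midline and endline outcomes, with baseline suppression as a covariate.
2. Constrain the arms to a common baseline mean in a mixed or GLS model that specifies the within-person covariance. In simulation its relative variance was 0.91, 0.77 and 0.50 at rho 0.32, 0.50 and 0.69, the same as the baseline-adjusted endline model.

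Merely dropping P_i from the stated single-error regression is not enough: without X_i it returns the crude endline difference.

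The cost is one degree of freedom and some wording. No new data are needed.
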